The two-sided p values for the least square mean (LSM) difference between the ECF843 and corresponding vehicle group will be reported for primary inference.Line plots (LSM  $\pm$  1 SE) will be presented by treatment groups and post-baseline day/visit. The x-axis will be study day/visit and the y-axis will be the change from baseline value.

#### 2.5.3 Handling of missing values/censoring/discontinuations

For other missing values not related to intercurrent event, the primary MMRM model implicitly imputes missing data under a MAR assumption.

#### 2.5.4 Supportive analyses

The subgroup analyses will be conducted to assess the consistency of treatment effect across various subgroups described in Section 2.2.1. Subgroup analyses will be conducted using the same model and analysis strategies described in the primary analyses but fitted by category of each of the subgroups. Subgroup variables that are used as fixed effects in the model will be removed from the model statement in the subgroup analysis if applicable. Subgroups will be presented graphically using forest plots. If a subgroup has limited number of subjects, the analyses on this subgroup may fail to converge and not be implemented. Instead, summary statistics for subgroup will be provided.

The summary statistics (mean, median, 25th percentile, 75th percentile, standard deviation, minimum and maximum, the number of non-missing observations, and 95% confidence interval) for change from baseline in SANDE symptom score and composite corneal fluorescein staining will be provided by treatment group for each post-baseline visit

Line plots with error bar (mean  $\pm 1$  SE) will be presented by treatment groups and all postbaseline visits Subgroup summary and plot will also be presented.

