#### 2.2.1 Subgroup of interest

The subgroups of interest are specified below:

- Baseline age group: < 65 years, and >=65 years
- Sex: male, female
- Documented diagnosis of Sjogren's syndrome: yes, no
- Race: asian, non-asian

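### SAP 2.5.4 aims to assess subgroup consistency but plans no estimate of the difference in treatment effect between categories, and no criterion for judging it

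*SAP*

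**What the plan says.** SAP 2.5.4 gives the purpose: "The subgroup analyses will be conducted to assess the consistency of treatment effect across various subgroups". SAP 2.2.1 lists four factors with two categories each: age ("Baseline age group: < 65 years, and >=65 years"), sex ("Sex: male, female"), Sjögren's status ("Documented diagnosis of Sjogren's syndrome: yes, no") and race (Asian or not). It gives no expected category sizes.

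The method is to refit the primary model "using the same model and analysis strategies described in the primary analyses but fitted by category of each of the subgroups". On display, the SAP says "Subgroups will be presented graphically using forest plots". For a category with few subjects it warns that "the analyses on this subgroup may fail to converge and not be implemented", in which case summary statistics take its place.

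The primary strategy includes an ordered covariance fallback (SAP 2.5.2 and 5.2.1). For SANDE it is Toeplitz, then AR(1), then compound symmetry. For staining it is unstructured, then the same three.

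Nothing elsewhere supplies a between-category comparison. The model equations in SAP 5.2.1 contain no subgroup interaction, and protocol 12.4.6 leaves subgroup analyses to the SAP. The SAS call in SAP 5.2.1 is not visible in the public text, but the equations are, and the subgroup paragraph in 2.5.4 reads as complete.

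**The concern.** Whether an effect is consistent is a question about the difference between two category effects. The plan estimates each effect separately and stops there. Readers get two intervals per factor and no standard error for the quantity of interest, so they must judge by eye. A common and misleading shortcut is to note that one category is significant and the other is not.

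The separate fits create a second difficulty. Because the fallback sequence applies within each category, two categories of one factor can be estimated under different covariance structures. If one does not converge, it is described by summary statistics on raw values (SAP 2.1.1.8), while its counterpart has a model-based estimate under MAR. The two are then not like for like. Any small category is the most exposed. Sjögren's status could be such a factor, although it is the stratification factor in protocol 6.3.2.

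What is at stake is the interpretation of supportive results in a study meant to found further development (protocol 1.2). The primary inference is not at stake.

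**Working it through.** **Inputs.** SANDE difference 10 mm, SD 23 mm, 112 per arm, two-sided 5% adjusted for three comparisons (SAP 3.1.1). Staining difference 1, SD 1, 112 per arm (protocol 12.8.1). About 680 randomised (protocol 5) in five equal arms (protocol 6.1.3), so 680/5 = 136 per arm. Category splits are assumed, from 50:50 to 90:10 and equal across arms, because the documents give none. Calculations use the normal approximation at a single time point and ignore any gain from repeated measures.

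**Reproducing the plan's figure.** SE = 23 × √(2/112) = 3.07 mm, and 10/3.07 = 3.25. At 0.05/3 the critical value is 2.39, so power = Φ(3.25 − 2.39) ≈ 80%, as stated. The 15 cells of SAP Table 3-1 reproduce within one percentage point.

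**If significance per category were the yardstick.** Give both categories the same true effect and let p1 and p2 be their powers. The chance that exactly one is significant is p1(1 − p2) + p2(1 − p1).

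Example, SANDE at 50:50 with 112 per arm: 56 per arm per category, SE = 23 × √(2/56) = 4.35 mm, 10/4.35 = 2.30, power 63% at 0.05. Discordance = 2 × 0.63 × 0.37 ≈ 46%.

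At 90:10 the powers are 87% and 18%, so discordance = 0.87 × 0.82 + 0.18 × 0.13 ≈ 74%.

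The SAP does not say whether the Hochberg adjustment carries into the subgroups, so 0.05 and 0.05/3 are both shown.

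| Endpoint, n per arm, level | 50:50 | 70:30 | 80:20 | 90:10 |
|---|---|---|---|---|
| SANDE, 112, 0.05 | 46% | 54% | 63% | 74% |
| SANDE, 112, 0.05/3 | 50% | 56% | 63% | 71% |
| SANDE, 136, 0.05 | 41% | 50% | 61% | 75% |
| SANDE, 136, 0.05/3 | 49% | 58% | 67% | 77% |
| Staining, 112, 0.05 | 0.1% | 1.6% | 8% | 34% |
| Staining, 112, 0.05/3 | 0.4% | 4% | 17% | 51% |
| Staining, 136, 0.05 | <0.1% | 0.5% | 4% | 26% |
| Staining, 136, 0.05/3 | 0.1% | 1.7% | 10% | 42% |

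The SANDE rate also depends on the true effect. At 112 per arm and 0.05 it is 19% (50:50) to 69% (90:10) for 14 mm, 33% to 37% for 5 mm, and 9.5% for no effect.

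**If the forest plot were read in other ways.** For SANDE at 10 mm with 112 per arm, estimates of opposite sign occur in 2% (50:50) to 15% (90:10) of comparisons. Non-overlapping 95% intervals occur in 0.6% to 1.3%.

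**What the missing estimate would offer.** With a share f of each arm in one category, the interaction SE = √[2 × 23²/112 × (1/f + 1/(1 − f))].
- 50:50: √(9.45 × 4) = 6.1 mm; power for a 10 mm difference in effects is about 37%.
- 90:10: √(9.45 × 11.1) = 10.2 mm; power is about 16%.

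The false-flag rate is 5% per test at any split and for either endpoint. With 4 factors × 3 comparisons × 2 endpoints = 24 tests, 24 × 0.05 = 1.2 false flags are expected if all are read at 5%.

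**The case against.** The strongest reply is that the SAP sets no significance rule. It plans forest plots, and with those a reader can compare estimates and intervals. Under the SANDE assumptions, intervals that fail to overlap would be rare when the effects are equal. This stands: the 41% to 75% describes a likely misreading, not a rule in the plan.

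A reader might go further and infer that half or more of all subgroup comparisons would look inconsistent. The documents do not support that. Half of the 24 comparisons concern staining, where the rate is far lower. Averaging the two endpoints at 112 per arm and 0.05 gives about 23% at 50:50, 28% at 70:30 and 35% at 80:20, and passes one half only near 90:10. Nor do the documents say that the Sjögren's or Asian category is small.

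A reader might also infer that the plan cannot answer its own question. That is too strong. The categories contain different subjects, so where both models converge the difference d1 − d2 has SE √(se1² + se2²) and can be computed from the planned output. What is missing is a commitment to report it.

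The convergence problem is partly anticipated, since the fallback order is pre-specified and the resort to summary statistics is disclosed. That does not make the two categories comparable when they stop at different steps.

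Finally, the analyses are supportive, and no stated decision, including starting Part 2, depends on them. An interaction test would have low power. Both points are right. The second argues for reporting an interval rather than relying on a p-value.

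**Conclusion.** The concern holds in this form: the aim is consistency, but the plan specifies no interaction, no between-category difference with an interval and no criterion. Separate fits can also leave categories of one factor estimated on different footings.

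The numerical consequence is conditional. If per-category significance were compared at the two-sided 5% level, with an identical 10 mm effect, SD 23 mm, 112 to 136 per arm and assumed splits of 50:50 to 90:10, about 41% to 75% of SANDE comparisons would look inconsistent. For staining with 112 per arm the rate would be about 0% to 17% up to an 80:20 split and 34% to 51% at 90:10, across the two levels, and lower with 136 per arm.

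This is a worthwhile, inexpensive correction to an exploratory analysis. It does not touch the primary test or its error control.

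**What to change.** For each factor, fit one MMRM on FAS1 under the primary covariance structure, adding subgroup, treatment*subgroup and treatment*subgroup*visit (day for SANDE). Sjögren's status is already in the model and stays there. Take the category effects from this model. Beside the forest plot, report the between-category difference in treatment effect with its 95% CI at the time points used for the primary inference, labelled exploratory.

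Where the three-way term for daily SANDE is too sparse to fit, use the difference of the separately fitted estimates with SE √(se1² + se2²), with the same covariance structure in both categories.

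State in the SAP that precision is low (SANDE interaction SE about 6 to 10 mm), so a non-significant interaction does not demonstrate consistency.

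The cost is SAP wording and modest programming; no new data are needed. The downsides are an assumed common covariance across categories, low power, and about 1.2 expected false flags if all 24 tests are read at 5%.

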#### 2.5.4.1 Supplementary estimand

The target population, the primary variable and the summary measure of this estimand are the same as for the primary estimand. The supplementary estimand is defined to estimate the treatment effect of ECF843, regardless of occasional rescue use of artificial tears/gels/lubricants, prohibited medications and treatment discontinuations.

The justification for the supplementary estimand is that they will capture the effect of the study drug when administered in the real world with intercurrent events considered as inherent in the treatment regimen.

# Table 2-5The handling of intercurrent events strategy for supplementary
estimand

Intercurrent Events	Strategy
Artificial tears/gels/lubricants for occasional rescue use	
 
All observed data will be used for analysis
 

	
 
Missing data on the days of IEs, if any, will be multiple imputed under MAR assumption
 

Prohibited medications that could confound the primary endpoint (See Table 2-3)	
 
All observed data will be used for analysis
 

 
Ocular, nasal, inhaled, or systemic corticosteroids
 
	

Intercurrent Events	Strategy
Intravitreal injections of any kind	
 
Missing data on the days of IEs + 3 days, if any, will be multiple imputed under MAR assumption
 

 
Any topical ocular medications (prescription or over the counter; excluding IOP-lowering medication)
 
Medical device treatments such as those used to treat Meibomian gland dysfunction (eg, LipiFlow, pulse light therapy, etc)
 
Punctal plugs or punctal cauterization
 
	
 
All observed data will be used for analysis
 
Missing data on the days of IEs, if any, will be multiple imputed under MAR assumption
 

Discontinuation of study treatment	
 
RDO data collected after study treatment discontinuation will be used for analysis.
 
Missing data after the treatment
 

	discontinuation, if any, will be multiple imputed based on J2R assumption for the ECF843 arms and under MAR assumption for vehicle arms

#### 2.5.4.2 Sensitivity Analysis

Not applicable.

# 2.6 Analysis of the key secondary objective

There is no key secondary objective in either Part 1 or Part 2 of the study.

# 2.7 Analysis of secondary efficacy objective(s)

#### 2.7.1 Secondary endpoints

The second efficacy objective is to evaluate the improvement of ECF843 vs vehicle in corneal damage by quadrant. The analysis of the secondary endpoints will be based on FAS 1.

•	Change from baseline in central corneal fluorescein staining
•	Change from baseline in inferior corneal fluorescein staining
•	Change from baseline in tear breakup time (TBUT)
•	Change from baseline in conjunctival lissamine staining score

# 2.7.2 Statistical hypothesis, model, and method of analysis

No statistical hypothesis test will be performed. The summary statistics (mean, median, 25th percentile, 75th percentile, standard deviation, minimum and maximum, the number of non-missing observations, and 95% confidence interval) for change from baseline in inferior and

central corneal fluorescein staining will be provided by treatment group for each post-baseline visit.

A 95% confidence interval will be provided for the difference between the ECF843 arm and its corresponding vehicle at each post-baseline visit.

# 2.7.3 Handling of missing values/censoring/discontinuations

All observed data will be used for analysis and missing data will not be imputed.

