2.2 Secondary Estimands

Not applicable.

3 Study design

Figure 3-1 Study Design

The study will be conducted in 2 parts: **Part 1** – efficacy and safety of ECF843 vs vehicle, followed by **Part 2** – additional exploratory assessments of ECF843 vs Vehicle. Both parts of the study include a double-masked study design, with randomization stratified for subjects with Sjogren's Syndrome.

In Part 1 subjects will be randomized to receive twice daily (BID) or three times daily (TID) treatment with either ECF843 or vehicle for 56 days. For subjects randomized to ECF843, the maximum drug exposure will be up to 28 days. At some point during Part 1, all subjects will receive vehicle. The study will be conducted in a way that neither the Investigator nor the subject are aware of the criteria for qualification into the primary efficacy analysis, nor the period(s) during which vehicle treatment is assigned. There will be a database lock after all subjects have completed their participation in Part 1 of the study. The data will be analyzed to determine the efficacy and safety of ECF843 vs vehicle and selection of the optimal concentration and posology. Part 1 must be fully completed prior to initiating Part 2. Part 2 will be initiated only if safety and efficacy of ECF843 during Part 1 is demonstrated.

Between the end of the subject's participation in Part 1 and the beginning of participation in Part 2, subjects will be treated as needed and according to Investigator judgement, and no protocol assessments or proactive solicitation of adverse events will be collected. If a subject spontaneously reports a serious adverse event (SAE) within 30 days of completing Part 1, those events will be captured as stated in Section 10.1.3.

Only subjects assigned exclusively to vehicle treatment in Part 1 may be eligible to participate in Part 2 of the study. A list of subjects eligible for screening in Part 2 of the study will be discussed between the Investigator and the Sponsor prior to initiating screening visits. In the event a study site was initiated close to the end of enrollment and did not have sufficient time to begin recruiting subjects, the site may enroll subjects into Part 2 of the study if approved by the Sponsor.

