8.3.3 Corneal Fluorescein Staining

Corneal fluorescein staining will be conducted by the Investigator. For individual subjects, corneal fluorescein staining should be assessed by the same examiner at all visits using the same slit lamp and the same settings. The right eye should be completed first, followed by the left eye.

[figure not shown]
At visits where TBUT is also done, instillation of the sodium fluorescein dye will have already occurred. As long as the corneal staining assessment is done within the specified time frame, no additional instillation of fluorescein dye is required. At visits where TBUT is not done, follow the same procedure as described above for instillation of fluorescein dye to each eye.

Staining will be assessed a minimum of 2.5 minutes and preferably less than 5 minutes after instillation of the dye. Evaluation of the cornea will be done through a slit lamp with use of a cobalt blue filter.

The degree of staining is based on the Corneal Fluorescein Modified NEI Scale. Each of the five regions (as depicted in the diagram, and defined as central (C), superior (S), inferior (I), temporal (T), and nasal (N)) will be graded based on a scale of 0 to 4, with higher scores suggestive of higher degrees of corneal staining (Figure 8-2). The examiner will indicate the appropriate score for each region. If the assessment falls between grades, round up to the higher score. After entry of the scores per region, the total or composite (sum) score for each eye will be automatically calculated (maximum score = 20/eye).

A (+1) will be added to the sum score for any eye with the presence of filaments.

Figure 8-2 Corneal Fluorescein Modified NEI Scale

Grade 0	No staining
Grade 1	Superficial micropunctate staining covering < 25% of the corneal surface
Grade 2	Macropunctate staining AND/OR superficial micropunctate staining covering 25-50% of the corneal surface
Grade 3	Some coalesced macropunctate staining AND/OR superficial micropunctate staining covering 51-75% of the corneal surface
Grade 4	Numerous coalesced macropunctate areas and/or patches AND/OR superficial micropunctate staining covering > 75% of the corneal surface

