12.4.4 Handling of missing values not related to intercurrent event

For all analyses, imputation of intermittent missing observations before discontinuation from study treatment will be carried out following a MAR mechanism for all treatment arms.

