#### 2.5.1 Primary endpoints

The primary clinical question of interest is: What is the effect of ECF843 versus its corresponding vehicle on change from baseline in signs and symptoms after treatment in subjects with moderate to severe DED, had they not taken occasional rescue use of artificial tears/gels/lubricants, prohibited medications and behaved like other subject who did not take them, had they not dicontinued treatment and behaved like other subjects who did not discontinue treatment?

The justification for the primary estimands is that they will capture the effect of the study drug when administered without confounding effects from prohibited medications, occasional

rescue use of artificial tears/gels/lubricants, and adjusting for unfavorable outcome treatment discontinuation

The analysis of the primary estimands will be based on FAS 1.

The primary estimand is defined as follows for signs and symptoms:

- The target **population** is subjects with moderate to severe DED who meet the inclusion and exclusion criteria
- The primary **endpoints** are the change from baseline in SANDE score and change from baseline in composite corneal fluorescein staining score
- The **treatment of interest** is ECF843 versus vehicle had they not needed occasional rescue use of artificial tears/gels/lubricants, prohibited medications and behaved like other subjects who did not take them, and had they not dicontinued treatment and behaved like other subjects who did not discontinue treatment.

Table 2-4	The handling of intercurrent events strategy for primary estimands
-----------	--

Intercurrent Events	Strategy
Artificial tears/gels/lubricants for occasional rescue use	
 
The data on the days will be excluded and treated as missing.
 

	
 
Missing data will be under MAR assumption in MMRM
 

 
Prohibited medications that could confound the primary endpoint (See Table 2-3)
 
Ocular, nasal, inhaled, or systemic corticosteroids
 
	
 
The data on the day(s) + 3 days following the last day of these prohibited medications will be excluded and treated as missing.
 

Intravitreal injections of any kind	
 
Missing data will be under MAR assumption in MMRM
 

 
Any topical ocular medications (prescription or over the counter; excluding IOP-lowering medication)
 
	
 
The data on the days of prohibited medications will be excluded and treated as missing.
 

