
 
Medical device treatments such as those used to treat Meibomian gland dysfunction (eg, LipiFlow, pulse light therapy, etc)
 
	
 
Missing data will be under MAR assumption in MMRM
 

Punctal plugs or punctal cauterization	
Discontinuation of study treatment	
 
The data after study treatment discontinuation will be treated as missing.
 

	
 
Missing data after study treatment discontinuation will be based on the MAR assumption in MMRM
 

- The **summary measure** is the treatment difference of the variable means between ECF843 and vehicle within each dose regimen (BID or TID) respectively.
  - ECF843 0.45mg/ml, TID vs ECF843 vehicle, TID
  - ECF843 0.15mg/ml, TID vs ECF843 vehicle, TID

Novartis	For business use only	Page 19
SAP		CECF843A2201

• ECF843 0.15mg/ml, BID vs ECF843 vehicle, BID

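### Central and inferior corneal staining are summarised on all observed exams without a model, while the composite that contains them is analysed after intercurrent-event exclusions in an MMRM, so the two effects answer different questions

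*SAP*

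**What the plan says.** **Composite, primary analysis.** Protocol 8.3.3 grades five corneal regions from 0 to 4 at one exam and sums them, adding 1 if filaments are present. SAP Table 2-4 (also Protocol 12.4.3) removes some of these exams:

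- Rescue artificial tears: "The data on the days will be excluded and treated as missing". Other topical ocular medication, device treatment and punctal plugs are handled in the same way.
- Corticosteroids and intravitreal injections: the days of use plus three further days are removed.
- Treatment discontinuation: "The data after study treatment discontinuation will be treated as missing".

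The rest goes into an MMRM under MAR (SAP 2.5.2 and 5.2.1).

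**Composite, supplementary analysis.** SAP Table 2-5 takes the opposite approach to intercurrent events: "All observed data will be used for analysis". Missing values are then imputed under MAR, or under J2R in the ECF843 arms after discontinuation, and the MMRM is fitted.

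**Central and inferior staining.** SAP 2.7.2 gives summary statistics and a 95% CI for the difference from vehicle at each visit, and says "No statistical hypothesis test will be performed". SAP 2.7.3 adds: "All observed data will be used for analysis and missing data will not be imputed". Protocol 2.2 marks secondary estimands as not applicable.

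**The concern.** A reader of the report will set the regional differences beside the primary composite difference to see where on the cornea any effect lies. The two come from the same exams, but they differ in three ways: which exams count, whether missing exams are modelled, and whether the difference is adjusted for baseline score and Sjögren's stratum.

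The regional result is in effect treatment policy on observed cases. It is not the hypothetical strategy, because intercurrent-event exams stay in. It is not the full Table 2-5 strategy either, because there is no imputation and no model. With no secondary estimand, nothing tells the reader which question the interval answers. A weaker regional effect could then reflect data handling rather than location.

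**Working it through.** **1. The plan's own figure.** Protocol 12.8.1 assumes a composite difference of 1 with SD 1 and 112 subjects per arm, and states more than 99% power at two-sided 5% adjusted for three comparisons.

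- Standard error: 1 × √(2/112) = 0.134, so the standardised difference is 1/0.134 = 7.48.
- Critical value at 0.05/3 two-sided: 2.39.
- Power: Φ(7.48 − 2.39) = Φ(5.09), above 99.99%. The figure reproduces and is not in dispute.

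**2. Scale of a regional effect (assumption).** Spread evenly, a composite effect of 1 is 1/5 = 0.20 grade per region. The documents give no regional effect.

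**3. Dilution from keeping intercurrent-event exams.** Let q be the share of ECF843 exams affected and r the fraction of the drug effect retained there. Neither is in the documents. The all-observed effect is 0.20 × (1 − q + q × r).

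| q | r = 1 | r = 0.5 | r = 0 |
|---|---|---|---|
| 5% | 0.200 | 0.195 | 0.190 |
| 10% | 0.200 | 0.190 | 0.180 |
| 20% | 0.200 | 0.180 | 0.160 |

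The loss runs from 0 to 0.04 grade for q up to 20%. A simulation of five regions under both rules agrees. With r = 0 and q = 5%, 10% and 20%, the composite stays near 1.00 after exclusion but falls to 0.95, 0.90 and 0.80 on all observed data.

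**4. Unequal rescue use.** Suppose rescue improves the composite by b points at affected exams. The all-observed composite effect is 1 + b × (share in ECF843) − b × (share in vehicle).

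- 5% in both arms: no gap.
- 5% against 20% with b = 1: 1 + 0.05 − 0.20 = 0.85, a gap of 0.15/5 = 0.03 grade per region.
- The same shares with b = 2: 0.70, a gap of 0.30/5 = 0.06 grade per region.

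**5. Dropout that depends on earlier staining.** Simulation settings, all assumed: 2,000,000 per arm, true difference −0.20 at the later visit, SD 0.6, correlation 0.6 between visits, and logistic dropout on the earlier value with slope 2. The entries are the bias of the observed-case difference over repeat runs.

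| Effect already present at the earlier visit | 10% dropout | 18% dropout |
|---|---|---|
| Full | about 0.010 | 0.015 to 0.017 |
| Half | 0.004 to 0.006 | about 0.007 |
| None | about 0 | about 0 |

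Conditioning on the earlier visit, as an MMRM does, returned about −0.20 in every case.

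**6. Against sampling error.** With SD 0.6 and 112 per arm, the 95% half-width is 1.96 × 0.6 × √(2/112) = 0.157, about 0.16 grade. Every shift above is well below it.

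**The case against.** The strongest reply is that the SAP carries out what the protocol asks for. Protocol 12.5.1 plans summary statistics, counts of non-missing observations and a per-visit interval for these endpoints, with no test. SAP 3.2 confirms that they are not powered. The SAP uses the same observed-data rule for patient-reported outcomes (2.11) and exploratory endpoints (2.13), so it is a consistent convention. That stands, and it limits the weight of the point. It does not say what question an interval for a treatment difference answers.

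Nearer comparators are also planned. SAP 2.5.4 gives per-visit composite summaries, SAP 2.1.1.8 uses raw values for summary statistics, and the supplementary estimand keeps all observed data. This also stands, but none of these is the primary composite result, and the supplementary one is imputed and modelled.

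Few exams may be affected. Staining is graded only at visits, and most rescue and prohibited-treatment exclusions cover only the days of use. Protocol 9.1.1 sets only treatments and adverse events as the minimum data after discontinuation. This is plausible but not certain. The same section has discontinued subjects agreeing to return for end-of-treatment and follow-up visits. Device treatment and new punctal plugs lead to treatment discontinuation (Protocol Table 6-2), after which the primary analysis drops all later data.

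A reader might also infer that the SAP breaches Protocol 12.4.4, which says "For all analyses, imputation of intermittent missing observations before discontinuation from study treatment will be carried out following a MAR mechanism for all treatment arms", without declaring the change in SAP section 4. The documents do not establish that. Section 12.4.4 sits under the analyses for the primary objectives, and its opening words can be read as covering only those. The scope is arguable and worth clarifying.

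**Conclusion.** The mismatch holds: the regional effects and the primary composite effect rest on different exams and different methods, no reason is given, and they need not be comparable.

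Two stronger readings are not supported. First, one might infer that the regional and composite effects will disagree. The gap is zero if the effect is retained at affected exams, and otherwise depends on rates the documents do not give. Second, one might infer that the regional effects ought to add up to the composite. Only two of the five regions are secondary endpoints and filaments add a point, so they would not sum to it under any rule.

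The size is probably small. On an assumed 0.20 grade, dilution is 0 to 0.04 with up to 20% of exams affected, and dropout bias is about 0 to 0.017. Larger gaps need stronger assumptions, such as the 0.06 with markedly unequal rescue use and a two-point benefit. No primary conclusion or type I error rate is touched. This is a low-cost improvement to the interpretation of a descriptive secondary endpoint.

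**What to change.** Keep the SAP 2.7.3 sentence for the descriptive summaries of all secondary endpoints. SAP 2.7.1 also lists TBUT and lissamine staining, which would otherwise lose their missing-data rule. Then add to SAP 2.7.2/2.7.3:

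> For central and inferior corneal staining, the ECF843–vehicle difference and 95% CI at each visit will be estimated with the MMRM used for the composite (own baseline score, Sjögren's stratum, visit, treatment and interactions), with the intercurrent-event handling of Table 2-4 and missing data under MAR. The all-observed summary is supportive and descriptive.

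This fits Protocol 12.5.1, which asks for an interval for the difference but does not fix the method. If the sponsor prefers a treatment-policy reading for the regions, the SAP should say so and pair them with the supplementary composite. The choice should be made before Part 1 is unmasked, and one line should state whether Protocol 12.4.4 reaches beyond the primary endpoints.

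Cost: the existing program is run on two more variables, with a little extra programming, and slightly fewer exams enter each regional estimate. No hypothesis test is added.
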